The clinical benefit rate set forth in Section 10.4 does not capture Patients who achieve a complete response (CR) or partial response (PR) prior to 16 weeks from start of treatment if they cannot get a confirmatory response assessment completed by week 16.

By achieving at least a CR or PR, the patient is receiving a clinical benefit with BGJ398, regardless of confirmatory response. In order to address patients who achieved unconfirmed CR or PR, further exploration of all responses and analysis of all response versus the clinical benefit rate as defined per protocol Section 10.4 is warranted.

This study observed 6 unconfirmed and 5 confirmed responses among the following tumor types: HNSCC, Ovarian, Bladder, NSCLC Squamous, Glioblastoma and Cholangiocarcinoma. Among the six unconfirmed responses, three unconfirmed responses would fit the criteria mentioned above. Therefore, in conjunction with showing clinical benefit rate, treatment with BGJ398 could represent a significant improvement in the medical management for the aforementioned six tumor types.

The main objectives of this amendment are:

- Re-open the enrollment for patients with six tumor types, HNSCC, Ovarian, Bladder (urothelial cell carcinoma), NSCLC Squamous, Glioblastoma multiforme and Cholangiocarcinoma
- To align with the BGJ398 Clinical Development program
- clarifications, operational aspects, administrative changes and corrections

The amendment contains changes to: re-open enrollments for patients that have the six tumor types which are, HNSCC, Ovarian, Bladder, NSCLC Squamous, Glioblastoma and Cholangiocarcinoma. Enrollment of each tumor cohort will remain open until each tumor types successfully enrolls 10 patients per cohort evaluable for futility analysis.

Changes to the Protocol

Changes to specific sections of the protocol are shown in the track changes version of the protocol using strike through red font for deletions and red underlined for insertions.

Protocol Summary Section updated to match the body of the protocol.

The following changes were implemented throughout the protocol:

Section 1.2.1.2.1

- Updated with more current information

Section 2.1

- Added rationale for reopening the study with 6 tumor types, HNSCC, Ovarian, Bladder, NSCLC Squamous, Glioblastoma and Cholangiocarcinoma
- Removed reference for FGF ligand alteration

Table 3-1

- Clarification added for endpoint.

Section 5.1, Section 5.2

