5.1 Patient population

The study population will consist of 70- 120 adult patients with a diagnosis of a solid tumor or hematological malignancy that has been pre-identified as having FGFR genetic alterations. Patients with history/current evidence of tumor-induced osteomalacia (TIO) and FGF23-mediated hypophosphatemia with or without identification of an FGFR genetic alteration in the tumor will be allowed. Patients must have received at least one prior treatment for their recurrent, metastatic and/or locally advanced disease and have no remaining standard therapy options anticipated to result in a durable response. Patients must have progressive and measurable disease (per RECIST 1.1 or other appropriate hematological response assessment criteria) and be in need of treatment. For patients with TIO diagnosis, the presence of measurable or evaluable disease is not required provided there is evidence of FGF23-mediated hypophosphatemia (TIO patients will not be included in protocol amendment 3). This is a signal seeking study, attempting to identify additional patient populations who may benefit from treatment with single agent BGJ398.

Additional tumor types may be excluded during the course of the study at the discretion of Novartis. With Amendment 3, the study is re-opening for enrollment for the following six tumor types only: Head and Neck Squamous Cell Carcinoma, Bladder Cancer, Ovarian Cancer, Non-small cell lung carcinoma – Squamous, Glioblastoma with multiforme with FGFR 1-4 genetic alterations and Cholangiocarcinoma.

Patients must not have central nervous system (CNS) metastasis, leptomeningeal carcinomatosis, symptomatic cardiac disease, or impairment of gastrointestinal (GI) function. Patients must have archival tissue available for submission to allow for molecular testing related to pathway regulation. If tissue is not available or not of sufficient quantity the patient must be willing to undergo a fresh tumor biopsy to allow for this analysis. [REDACTED]

[REDACTED]

Note: An archival or fresh tumor sample may not be required if the patient has had their genomic profiling performed at a laboratory selected by Novartis and the patient has agreed to allow Novartis to use baseline molecular analysis results.

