Enrollment is meant to encompass solid tumors and hematologic malignancies as having FGFR genetic alterations that may be inhibited by BGJ398 who otherwise meet all of the inclusion and none of the exclusion criteria. Amendment 3: no longer allows for patients with FGF ligand amplification or TIO diagnosis to be included. Though common for phase I studies, tissue-agnostic enrollment is unusual for phase II studies, which typically limit enrollment to one or a few well-defined tumors types. We expect that the study will enroll patients whose tumors have already been pre-identified to harbor FGFR genetic alterations such as Breast, Gastric, Esophageal, Colorectal, and Squamous Head and Neck cancers (the amendment 3 limits the tumor types from Head and Neck Squamous Cell Carcinoma, Bladder Cancer, Ovarian Cancer, Non-small cell lung carcinoma – Squamous, Glioblastoma with multiforme with FGFR 1-4 genetic alterations and Cholangiocarcinoma.). The total number of patients to be enrolled per tumor type will be based on an adaptive design. The adaptive design will be patient-sparing and allow the early closure of non-responding arms or arms where early success can be declared.

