9.4 Database management and quality control

This study will be using eCRFs and the designated CRO will review the data entered by investigational staff for completeness and accuracy. Electronic data queries stating the nature of the problem and requesting clarification will be created for discrepancies and missing values and sent to the investigational site via the EDC system. Designated investigator site staff are required to respond promptly to queries and to make any necessary changes to the data.

Concomitant treatments and prior medications entered into the database will be coded using the WHO Drug Reference List, which employs the Anatomical Therapeutic Chemical classification system. Medical history/current medical conditions and adverse events will be coded using the Medical dictionary for regulatory activities (MedDRA current version) terminology.

Data from the screening molecular analysis will be collected locally and entered directly onto the eCRF. Tissue samples for pathway activation confirmation will be analyzed centrally.

At the conclusion of the study, the occurrence of any protocol deviations will be determined. After this action has been completed and the data has been verified to be complete and accurate, the database will be declared locked and the data made available for data analysis. Authorization is required prior to making any database changes to locked data, by joint written agreement between the US Oncology Medical Affairs Franchise Head and the US Oncology Medical Affairs Franchise Vice President.

After database lock, the investigator will receive a CD-ROM or paper copies of the patient data for archiving at the investigational site.

10 Statistical methods and data analysis

All data except the primary efficacy variable clinical benefit rate will be analyzed by a designated CRO in collaboration with Novartis. The analysis of the clinical benefit rate will be performed by a separate CRO using the Bayesian adaptive design approach described in details in [Appendix R](#). Any data analysis carried out independently by the investigator should be submitted to Novartis before publication or presentation. The data from all centers that participate in this study will be combined in the final safety and efficacy analysis.

This trial will enroll patients from at 6 histologic groups:

- NSCLC - Squamous
- Ovarian
- Glioblastoma Multiforme
- Squamous Head and Neck
- Bladder
- Cholangiocarcinoma

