10.1 Analysis sets

10.1.1 Full Analysis Set

The Full Analysis Set (FAS) will include all patients who have received at least one dose of the study drug.

FAS will be used for the analysis of all efficacy endpoints.

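### Six cohorts were re-opened because responses had been seen in them, and no analysis separates those patients from later ones: ORR is directly inflated, the CBR success rule only modestly

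*Protocol*

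**What the plan says.** **Why the cohorts re-opened.** The Amendment 3 rationale states: "This study observed 6 unconfirmed and 5 confirmed responses among the following tumor types". It infers that treatment "could represent a significant improvement in the medical management for the aforementioned six tumor types". Protocol Section 5.1 carries this into the current text: "With Amendment 3, the study is re-opening for enrollment for the following six tumor types only". The rationale also explains that CBR misses early responders whose confirmation is not done by week 16, and adds: "Among the six unconfirmed responses, three unconfirmed responses would fit the criteria mentioned above". The enrolment target is: "Enrollment of each tumor cohort will remain open until each tumor types successfully enrolls 10 patients per cohort evaluable for futility analysis". Whether patients already enrolled count towards the 10 is not said.

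**Who is analysed.** Protocol Section 10.1.1: "The Full Analysis Set (FAS) will include all patients who have received at least one dose of the study drug". SAP Section 3.1 uses the same set. Protocol Section 4.2 and SAP Section 2 set one cut-off for all patients' data. Success is declared per tumour group on a posterior probability (Protocol Section 10.4.3, SAP Section 10.3). ORR is reported per group with an exact 95% interval (Protocol Section 10.5.1).

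**What is not planned.** Protocol Section 10.4.5 lists no supportive analysis of the primary endpoint. SAP Sections 2.1 and 6.2 to 6.4 offer separate summaries by cohort size, not enrolment period. The SAP (13 July 2017) postdates Amendment 3 (30 January 2017) but does not mention the re-opening. The simulation assumptions (Appendix R Section 14.4.4.1, SAP Section 10.4.1) contain no step at which observed responses decide which cohorts continue.

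**Eligibility.** Section 5.1 says that Amendment 3 "no longer allows for patients with FGF ligand amplification or TIO diagnosis to be included".

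**The concern.** A cohort chosen because it showed responses has, on average, a higher early response rate than its true rate. If the same patients enter the final estimate, that excess is carried along and only diluted by new patients. The thresholds and the stated error rates belong to a design without this step.

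The trial's aim is to decide whether further study is warranted. A reader of a positive re-opened cohort will want to know whether the signal recurs in patients who had no part in choosing the cohort, and the planned outputs cannot show this. The change in entry rules adds a second reason to separate the periods. Ligand amplification no longer qualifies. The Amendment 1 summary records that urothelial carcinoma, cholangiocarcinoma and glioblastoma with FGFR 1-4 alterations then entered only case by case, whereas Section 5.2 now admits them without prior approval. That is not a contradiction, but it means that early and late patients in a cohort may differ.

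**Working it through.** **1. The plan's own figures.** The Appendix R model was simulated: Dirichlet process mixture with concentration 2, the prior for μ read as variance 3.24 (1.8 squared), τ² ~ IG(3, 0.5), Poisson accrual, 1,500 trials per scenario, final analysis only. At a threshold of 0.80 and 10 per cohort it gives an average success probability of 0.152 under the null (Table 14-2 averages 0.144) and 0.928 under the alternative (0.920). At 5 per cohort it gives 0.147 (0.144) and 0.799 (0.812). The model is therefore a fair basis. At 0.90, the threshold in the protocol body and SAP, the null figure is about 0.06.

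**2. Assumptions that the documents do not supply.** 3, 5 or 8 early patients per cohort, topped up to 10 (or 5 topped up to 15); true ORR 0.05 to 0.20; null CBR 0.45, the Table 14-1 value for lung and HNSCC (the table has no rate for glioblastoma or cholangiocarcinoma). Two selection rules: (a) the six of 12 cohorts with most early responses; (b) one cohort re-opened if it had at least one response.

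**3. ORR, rule (b).** True ORR 0.10, 5 early and 5 new patients.
- P(at least one early response) = 1 − 0.9⁵ = 0.4095
- Mean early responses given re-opening = 0.5 / 0.4095 = 1.221
- Mean pooled ORR = (1.221 + 5 × 0.10) / 10 = 0.172

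Rule (a) gives 0.146 by simulation. New patients alone average 0.10. Under rule (a) the exact 95% lower limit lay above the true rate in 2.5% of cohorts, against 1.4% unselected, so the harm there is mainly to the point estimate.

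**4. CBR, rule (b), no borrowing.** Let w be the share of responders who count as clinical benefit. Three of the 11 responses are not captured, so w is at most 8/11 = 0.727. For a null cohort, the benefit probability among non-responders is q = (0.45 − 0.10w) / 0.90.
- w = 8/11: q = 0.419. Mean pooled CBR = (1.221 × 0.727 + 3.779 × 0.419 + 5 × 0.45) / 10 = 0.472, against a true 0.45. The cut-off for 0.90 is 7 of 10; exact false success is 0.126, against 0.102 unselected.
- w = 0.45: q = (0.45 − 0.045) / 0.90 = 0.45 = w. Knowing that a patient responded then says nothing about CBR, and the bias vanishes. This is close to 5/11 = 0.455, the case where only the confirmed responses count.

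**5. CBR, rule (a), with the planned borrowing.** False success per null cohort at the 0.90 threshold:

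| w | Early / total | True ORR | Unselected | Re-opened | Pooled ORR |
|---|---|---|---|---|---|
| 8/11 | 5 / 10 | 0.10 | 0.064 | 0.083 | 0.146 |
| 8/11 | 3 / 10 | 0.10 | 0.071 | 0.084 | 0.130 |
| 8/11 | 8 / 10 | 0.10 | 0.061 | 0.088 | 0.161 |
| 8/11 | 5 / 15 | 0.10 | 0.068 | 0.081 | 0.131 |
| 8/11 | 5 / 10 | 0.20 | 0.068 | 0.093 | 0.265 |
| 1 | 5 / 10 | 0.10 | 0.067 | 0.108 | 0.146 |

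For the first row, the 0.80 threshold gives 0.193 against 0.159, and the chance of at least one false success among six (at 0.90) is 0.333 against 0.282.

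**6. What new patients alone could show.** At 5 per cohort and a threshold of 0.90, the model's power under the Table 14-2 alternative is 0.634.

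**The case against.** **The effect on the primary endpoint is small.** This stands. Selection was on CR/PR, not on CBR. A reader might infer a larger inflation by letting every responder count (0.108 against 0.067) or by supposing that cohorts were picked on CBR itself (0.200 against 0.064). The amendment supports neither: it gives responses as the ground and says that three of them fall outside CBR. SAP Section 6.1 can lower the share further, since responders who progress before week 16 fail and those who stop early for other reasons are non-evaluable. The borrowing figures at 8/11 also sit below the 0.20 that the plan tolerates under the null.

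**The cohorts were not chosen by chance responses alone.** This stands in part. Alignment with the development programme is another stated objective, and Protocol Section 1.2.1.2.2 reports phase I activity in four of the six types. The calculations therefore describe null cohorts and do not claim that these six are null.

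**The purpose was to fill cohorts, not to replicate.** The amendment speaks of reaching 10 evaluable patients for futility and nowhere names replication as an aim. That weakens a charge of failed intent, but not the value of seeing the periods apart.

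**Pooling is not stated outright.** True. The sentence "The data from all centers that participate in this study will be combined in the final safety and efficacy analysis" concerns centres and does not settle it. The analysis-set definition and the single cut-off do, because neither excludes earlier patients.

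**The mutation summary covers the population change.** SAP Section 6.5 plans CBR by gene mutation, which helps, but it is not a split by period and omits ORR. How many ligand-only patients are in these cohorts is unknown.

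**Conclusion.** The point holds in a limited form. Re-opening on observed responses was unplanned and is outside the simulated operating characteristics. Patients from both periods are pooled without any analysis by period, under changed entry rules.

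The main distortion is in ORR: an average of about 0.15 to 0.17 where the truth is 0.10, for 5 early patients topped up to 10. For the CBR success rule it is modest: 0.083 against 0.064 with borrowing, 0.126 against 0.102 without, and near zero if only about half of the responders count as benefit. Direction is firm; size is conditional on assumed early cohort sizes, selection rule and response rates.

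A reader might go further and ask that any success also be met in new patients at the same threshold. The data could not bear that: with 5 new patients per cohort, about 37% of truly effective cohorts would miss 0.90 (1 − 0.634). The point is a cheap improvement, not a flaw that invalidates the primary analysis.

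**What to change.** Keep the pooled analysis as primary. Add to the SAP:

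1. A table of CBR and ORR with exact 95% intervals, by cohort, for patients enrolled before Amendment 3 and under it.
2. The same hierarchical model fitted to Amendment 3 patients only, as a supportive analysis that reports posterior probabilities and estimates with no pass/fail threshold.
3. A statement for the report that pooled results in the six cohorts are conditional on a re-opening prompted by observed responses.

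The cost is one table, one model run and a sentence of text. The drawback is imprecision: if earlier patients count towards the target of 10, some cohorts may have very few new patients. Missing a threshold in new patients must therefore not be read as refuting a signal, and the SAP should say so.

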Appendix P and Appendix Q

- Revised to align with the BGJ398 program

[figure not shown]
Appendix R and Appendix V

- Removed Appendix R and Appendix V as the revised appendices P and Q contain the information included in appendices R-V previously.

Minor inconsistencies, edits, and typographical errors that were identified after the finalization of the original protocol have been corrected with this amendment. IRB/IEC Approval

A copy of this amended protocol will be sent to the Institutional Review Board (IRBs)/Independent Ethics Committee (IECs) and Health Authorities.

The changes described in this amended protocol require IRB/IEC approval prior to implementation. In addition, if the changes herein affect the Informed Consent, sites are required to update and submit for approval a revised Informed Consent that takes into account the changes described in this amended protocol.

Amendment 1

Amendment rationale

The main purpose of this protocol amendment is to include endometrial tumors with FGFR 1-4 genetic alterations and FGF ligand amplifications that were previously excluded. Additionally, Urothelial cell carcinoma, Cholangiocarcinoma, and Glioblastoma multiforme with FGF Ligand amplifications are also allowed.

Also, to better understand the safety picture of BGJ398, Pharmacokinetic (PK) testing of BGJ398 and its metabolites has been added to the study. Collection of unscheduled blood (Plasma) PK samples will be collected in the event of an adverse event at the investigators discretion.

Changes to the inclusion/exclusion criteria:

Patients with endometrial tumors will be included. Urothelial cell carcinoma, Cholangiocarcinoma, and Glioblastoma multiforme with FGF ligand amplifications are allowed. Although Urothelial cell carcinoma, Cholangiocarcinoma, and Glioblastoma multiforme with FGFR 1-4 genetic alterations are excluded, these tumors may be considered on a case by case basis upon prior approval by Novartis.

Patients with molecular analysis performed at the confirmatory laboratory will not require additional tumor submission at time of study entry if subject has consented to allow transfer of information from pre-existing analysis to Sponsor.

Clarification of hematological requirements applicable for leukemia patients to be included due to compromised bone marrow system of this patient population. Patients with Leukemia will be included with peripheral blast counts $< 50,000$ blasts/mm³ to align with current standards.

Patients with clinical evidence of CNS leukemia will be excluded.

Patients who have received allogeneic stem cell transplant and/or have active graft -versus-host disease (GVHD) will be excluded.

Patients who have received autologous stem cell transplant within last 4 weeks will be excluded.

Exclusion #5 revised to add 'significant' to the history and/or current evidence of tissue calcification. It will read 'History and/or current evidence of **significant** tissue calcification including, but not limited to, the soft tissue, kidneys, intestine, myocardium and lung with the exception of calcified lymph nodes and asymptomatic coronary calcification.'

Exclusion # 31 was revised to indicate 'Patients with previous or concurrent primary malignancy within 3 years prior to starting study treatment, with the exception of adequately treated basal cell carcinoma, squamous cell carcinoma or other non-melanomatous skin cancer, or in-situ carcinoma of the uterine cervix treated curatively and without evidence of recurrence'.

Changes to the protocol

Changes to specific sections of the protocol are shown in the track changes version of the protocol using strike through red font for deletions and red underlined for insertions.

The following changes were implemented throughout the protocol:

Protocol summary “Purpose and rationale”, “Study design”, “Population”, Section 2.1 “Study rationale and purpose”, Section 2.2 “Rationale for the study design”, Section 4.1 “Description of study design”, Section 5.1 “Patient population”, Section 5.2 and Inclusion criteria number 3 removed the word “select”.

Section 2.1 and Section 5.1 were updated to clarify that Urothelial cell carcinoma, Cholangiocarcinoma, and Glioblastoma multiforme with FGFR 1-4 genetic alterations will be excluded, however these tumors may be included on a case by case basis upon prior approval by Novartis. Urothelial cell carcinoma, Cholangiocarcinoma, and Glioblastoma multiforme with FGF Ligand amplifications are allowed.

Section 7.2.3 ‘Pharmacokinetics’ was updated to allow for PK sample collection for BGJ398 and its metabolites.

Section 8.2.2 “Reporting” was update to provide guidance on SAE follow-up.

Section 5.1, Section 5.2, Section 7.1.1, and Section 7.2.4 were updated to include a Note indicating an archival or fresh tumor sample may not be required if the patient has had their genomic profiling performed at a laboratory selected by Novartis and the patient has agreed to allow Novartis to use baseline molecular analysis results.

Table 3-1 Primary endpoint was updated to indicate that, for hematologic tumors, other appropriate hematological response criteria will apply and are included in the appendices.

Section 7.1.4.3 was revised to indicate that the survival follow up may be done at the discretion of Novartis.

Section 7.2.1.1 was revised to add ‘For solid tumors, an assessment of PR or greater must be confirmed at least 4 weeks after initial observation using RECIST 1.1.’

Section 7.2.1.4 Leukemia was updated to add ‘For MF and PV, the Myeloproliferative Neoplasm (MPN) Symptom Assessment Form Total Symptom Score (MPN-SAF TSS) will be completed as is indicated in Table 7-1.’

Table 6-4 Follow-up for toxicity was updated with a revised language for the management of hyperphosphatemia.

Table 7-1 was updated to separately list the visit schedules of Myelofibrosis and Polycythemia vera.

Table 7-1 was updated to add additional cardiac imaging at once a month for the first 4 cycles, if clinically indicated for subsequent cycles, and at EOT.

[REDACTED]

Section 8.2.2 Reporting was revised to remove ‘The follow up information should describe whether the event has resolved or continues, if and how it was treated, and whether the patient continued or withdrew from study participation.’

Section 9.4 Database management and quality control was revised to replace ‘violations’ with ‘deviations’ in the statement ‘At the conclusion of the study, the occurrence of any protocol deviations will be determined.’

Section 10 “Statistical methods and data analysis” updated section to be consistent with Appendix M. Added clarification on safety set. Clarified primary objective. Clarified handling of missing values. Clarified adverse event analysis. Clarified interim analysis and sample size calculation for consistency with Appendix M.

IRB/IEC Approval

A copy of this amended protocol will be sent to the Institutional Review Board (IRBs)/Independent Ethics Committee (IECs) and Health Authorities.

The changes described in this amended protocol require IRB/IEC approval prior to implementation. In addition, if the changes herein affect the Informed Consent, sites are required to update and submit for approval a revised Informed Consent that takes into account the changes described in this amended protocol.

[REDACTED]

1 Background

